#### 4.3 Exclusion Criteria

- o Patients suffering from urinary incontinence
- o Patients with overactive bladder
- o Patients with neurological bladder
- o Patients with active malignancies and who have been treated for malignancy in the previous 6 months

- o Patients suffering from local or systemic infections (UTI, osteomyelitis, sepsis, etc.)
- o Patients with renal insufficiency
- o Patients with bladder stones
- o Patients with gross haematuria

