With regards to imaging, renovesical ultrasound is recommended if, in addition to the LUTS mentioned above, there is hematuria or a history of kidney stones. Prostate ultrasound can be performed suprapublically or transrectally; it is essential to perform if surgery for BPH is planned, as the calculation of the prostate volume can decide which therapeutic procedure to perform [13]. The prostatic volume calculated by the suprapubic approach appears to be overestimated compared to that by the transrectal approach. Diagnostic cystoscopy is not recommended in patients with BPH.

Treatment of obstructive prostatic hypertrophy can be classified into three types:

- watchful waiting

-Pharmacological treatment

-surgical treatment

The choice of therapy is based on the severity/severity of symptoms estimated by the IPSS questionnaire.

In the presence of an IPSS score  $< 8$ , watchful waiting is possible (pharmacological therapy is not indicated). When the IPSS score  $> 8$ , it is indicated to start pharmacological therapy according to international guidelines. Surgery is confined to patients who do not respond to drug therapy and/or develop complications of an obstructive nature: obstructive renal failure, bladder stones with recurrent urinary tract infections, recurrent macroscopic haematuria.

Pharmacological treatment of prostatic hypertrophy mainly consists of alpha-blocker drugs, 5 alpha reductase inhibitors and herbal medicines.

$\alpha 1$ -blockers (e.g. tamsulosin, alfluzosin) aim to inhibit the effect of norepinephrine released on the smooth muscle cells of the prostate and thus aim to reduce the tone of the prostate and bladder neck [14]. These drugs also act on other receptors in other parts of the body, such as blood vessels, resulting in adverse effects, such as hypotension.

The different  $\alpha 1$ -blockers available on the market have similar efficacy in appropriate doses [16]. The effects take a couple of weeks to develop completely burned, but significant efficacy versus placebo can occur within hours or days [15].

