Controlled studies show that  $\alpha 1$ -blockers typically reduce IPSS by approximately 30-40% and increase Qmax by approximately 20-25% [17].  $\alpha 1$ -blockers do not reduce prostate size [18]. The most frequent adverse events of  $\alpha 1$ -blockers are asthenia, dizziness and orthostatic hypotension. They do not negatively affect libido, have a small beneficial effect on erectile function, but sometimes cause abnormal ejaculation [19]. Originally, abnormal ejaculation was associated with retrograde ejaculation, but more recent data show that it is due to a decrease or absence of seminal fluid during ejaculation.

Thus,  $\alpha 1$ -blockers are often considered the first-line pharmacological treatment of LUTS due to their rapid action, good efficacy, low frequency and severity of adverse events. However,  $\alpha 1$ -blockers do not prevent the onset of acute urinary retention and the need for surgery for BPH.

Another category of drugs involved in the treatment of BPH are the 5 alpha reductase inhibitors (5-ARIs). The effects of androgens on the prostate are mediated by dihydrotestosterone (DHT), which is converted from testosterone by the enzyme 5 $\alpha$ -reductase. There are two isoforms of this enzyme:

- 5 $\alpha$ -reductase type 1, activity predominant in extraprostatic tissues, such as skin and liver.

- 5 $\alpha$ -reductase type 2, predominant in the prostate.

Two 5-ARIs are available for clinical use: dutasteride and finasteride. Finasteride inhibits type 2 5 $\alpha$ -reductase only, whereas dutasteride inhibits type 1 and type 2 5 $\alpha$ -reductase with similar potency. 5 $\alpha$ -reductase inhibitors work by inducing apoptosis of prostate epithelial cells [20] leading to a reduction in prostate size by approximately 18-28% and a decrease in circulating PSA levels by approximately 50% after six to twelve months of treatment [21].

Placebo-related clinical effects are observed after a minimum treatment duration of at least six to twelve months. An indirect comparison and a direct comparative trial (twelve months duration) indicate that dutasteride and finasteride are equally effective in the treatment of LUTS [21, 23]. The greater the baseline prostate volume, the greater the symptomatic benefit of dutasteride over tamsulosin.

5 $\alpha$ -reductase inhibitors, but not  $\alpha$ 1-blockers, reduce the long-term risk (> 1 year) of acute urinary retention or the need for surgery [22, 24].

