## 2. Objectives of the study

The objective of this study is to evaluate the efficacy of the PEAPROSTIL 600 (FARMITALIA®) supplement composed of Serenoa Repens associated with PEA combined with alpha-blocker in the reduction of LUTS symptoms in patients with IBP. During the entire study period, any adverse events, intolerance, allergic reactions, complications related to the products used will be recorded.

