### 2.1 Primary Outcomes:

1) Evaluate the efficacy of the treatment in terms of subjective improvement of urinary symptoms by performing IPPS and SF-36 questionnaires and evaluate the objective improvement of urinary symptoms by performing uroflowmetry before and during treatment (during control visits follow-up at 1,3,6 and 12 months) by evaluation of the ultrasound post-voiding residue, comparing patients receiving combined therapy with tamsulosin+peaprostil (Arm 1) with patients receiving monotherapy with tamsulosin (Arm 3).

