## 3. Study design

The study is a single-center, 3-arm, prospective randomized clinical trial.

- Arm 1: PEAPROSTIL 600 + Tamsulosin 0.4 mg/dl
- Arm2: PEAPROSTIL 600
- Arm 3: Tamsulosin 0.4 mg

Upon enrollment in the study, each patient will be randomized into one of the 3 arms described. Randomization will take place in a 1:1:1 pattern.

Based on clinical-scientific considerations inherent to the typology of patients and to reality clinic, the experimental design indicated above currently corresponds to the best possible.

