### 4. Patient selection

#### 4.1 Target population

Patients referred to outpatient visits eligible for study at the S.C.D.U. of Urology of the Maggiore Hospital of Charity of Novara.

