#### 4.2 Inclusion criteria

- o Male patients aged 40 years or older
- o Patients with baseline IPSS questionnaire between 8 and 14
- o Patients with prostate volume  $\leq$  60 cc assessed by transrectal ultrasound (TRUS)
- o Patients who have a Qmax  $\leq$  15 ml/sec on uroflowmetry
- o Patients who show a post-voiding residue  $\leq$  120 ml on extemporaneous ultrasound
- o Patients who have signed the informed consent for participation in the study
- o Patients able to understand the conditions of the study and to participate for the full duration.

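### Sections 4.2 and 4.3 contain no exclusion for known hypersensitivity to a study product or known symptomatic orthostatic hypotension: a minor patient-safety gap that is cheap to close

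*Combined protocol and SAP*

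**What the plan says.** **Eligibility.** Section 4.3 has eight exclusions: urinary incontinence ("Patients suffering from urinary incontinence"), overactive bladder, neurological bladder, active or recently treated malignancy, infection, renal insufficiency, bladder stones and gross haematuria. Section 4.2 has seven inclusions: age, IPSS, prostate volume, Qmax, post-void residual, consent, and "Patients able to understand the conditions of the study and to participate for the full duration".

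**Allocation.** Section 3 states: "Upon enrollment in the study, each patient will be randomized into one of the 3 arms described". The ratio is 1:1:1. Arm 1 is PEAPROSTIL 600 plus tamsulosin, Arm 2 is PEAPROSTIL 600 alone, and Arm 3 is tamsulosin alone.

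**Known hazards.** On alpha-blockers, section 1 says: "These drugs also act on other receptors in other parts of the body, such as blood vessels, resulting in adverse effects, such as hypotension". It adds that their most frequent adverse events "are asthenia, dizziness and orthostatic hypotension". Section 5.3.2 lists fainting and angioedema among the rare effects of tamsulosin. For the products in general, section 2 says only that "any adverse events, intolerance, allergic reactions, complications related to the products used will be recorded".

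**Safeguards.** Section 5.2 collects allergies, current therapy and medical history at T0. Section 5.3.1 provides for treatment of an adverse event and, if needed, withdrawal. Section 5.4 puts the first scheduled check at 1 month.

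**The concern.** In routine care, a clinician who learns of an earlier reaction to a drug chooses a different one. In a randomised trial the allocation makes that choice, so eligibility is the point at which such a man has to be identified. Here the written criteria let him through, although the protocol itself describes the relevant tamsulosin effects.

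The stake is patient safety: a foreseeable and avoidable exposure of a man whose history already warns against the product. The treatment comparison is not at stake.

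**Working it through.** **1. Is the rule absent?** I read the seven inclusions and eight exclusions one by one. None refers to allergy, hypersensitivity, blood pressure, hypotension or syncope. The closest inclusion concerns understanding the study and taking part throughout, which is not a safety criterion. No other section of the text available supplies the rule.

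**2. Are the hazards in the documents?**
- *Tamsulosin:* yes. Hypotension and orthostatic hypotension are in section 1. Orthostatic hypotension appears again in section 5.3.2, with fainting and angioedema.
- *PEAPROSTIL 600:* only weakly. Section 2 mentions allergic reactions to the products in general. Section 1 describes the side effects of herbal agents as mild and similar to those on placebo.
- *Contraindications:* none is stated for any product. Moving from a listed effect to an exclusion is a clinical inference.

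**3. What happens before exposure?** Section 5.2 is headed as a pre-treatment assessment. It gathers the allergy, therapy and history data alongside IPSS, Qmax and residual, which are themselves inclusion measurements. The information is therefore collected at the right stage. What is missing is a written consequence for eligibility. Blood pressure is not a listed measurement at T0 or at follow-up, so the written plan would detect orthostatic hypotension only through the history.

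**4. Chance of allocation, given enrolment** (inputs: ratio and arm contents, section 3)

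| History | Arms containing the product | Probability |
|---|---|---|
| Hypersensitivity to tamsulosin | 1 and 3 | 1/3 + 1/3 = 2/3 |
| Symptomatic orthostatic hypotension (product concerned: tamsulosin) | 1 and 3 | 1/3 + 1/3 = 2/3 |
| Hypersensitivity to Serenoa repens or PEA | 1 and 2 | 1/3 + 1/3 = 2/3 |
| Hypersensitivity to both products | 1, 2 and 3 | 3 × 1/3 = 1 |

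These are chances of being allocated a product, not chances of harm.

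**5. Effect on the primary comparison.** Section 2.1 compares Arm 1 with Arm 3. Both contain tamsulosin, so a tamsulosin-related history bears on both sides alike. A PEAPROSTIL-related history would bear on Arm 1 only. However, section 6 specifies intention-to-treat analysis, and nothing in the documents suggests that such men are numerous.

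**6. Effect on power.** Reproducing the plan's figure first (section 6: difference 2, SD 4, significance level 0.05, taken as two-sided, power 90%):

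n per arm = 2 × (1.960 + 1.282)² × 4² / 2² ≈ 84.1, rounded up to 85. Over three arms this is 3 × 85 = 255, close to the stated 250.

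The exclusion acts before randomisation, so men screened out are replaced and 250 can still be randomised. As an illustration only, suppose 5 men in all were lost and not replaced:
- 250/3 = 83.33 per arm gives 89.4% power (two-sample t-test).
- 245/3 = 81.67 per arm gives 88.8% power.

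The loss is 0.6 percentage points.

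**The case against.** The strongest reply is that this is a routine drafting gap in a trial run by a single urology unit, where allergy and history are taken before treatment. No competent clinician would knowingly give tamsulosin to a man who has reacted to it. The documents also present the hazard as modest. Section 1 describes alpha-blocker adverse events as infrequent and not severe. Section 5.3.2 rates fainting and angioedema as rare (0.01-0.1%) and says that no serious adverse events have been reported in the literature with tamsulosin.

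Much of this stands. It makes the point minor, and it removes several stronger readings that a reader might infer:

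- **That the safeguards act only after exposure.** Section 5.2 does not support this. The relevant history is taken before treatment, and only the link to eligibility is missing.
- **That any such man has a 2/3 chance of exposure.** The 2/3 applies only once he is enrolled. Clinical judgement would probably stop many of these enrolments, so the overall chance is lower.
- **That the PEAPROSTIL hazard is as well documented as the tamsulosin hazard.** It is not, as step 2 of the working shows.
- **That the protocol contradicts itself.** It does not, because it states no contraindication. This is an omission.

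The reply does not remove the gap. Turning away a man who meets every written criterion is left to discretion. A written rule makes that decision consistent and open to audit. The rare rates in section 5.3.2 describe tamsulosin users in general and say nothing about men with a previous reaction.

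**Conclusion.** The point holds as a minor patient-safety omission. In the text available, a man with known hypersensitivity to a study product or known symptomatic orthostatic hypotension meets the written criteria. If enrolled, he has a 2/3 chance of being allocated the product concerned.

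The 2/3 is the only size that the documents support. They give no prevalence of either history among eligible men, so neither the number exposed nor the probability that at least one man is exposed can be stated. A reader might also infer a threat to the trial's result. The documents do not support that: there is no material effect on the primary comparison or on power.

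The conclusion rests on two assumptions. One is that no such exclusion stands in pages outside the text available. The other is the ordinary clinical judgement that a man with a known reaction to a product should not be randomised to a design that may give it to him. The tamsulosin part is well grounded in the protocol, and the PEAPROSTIL part is a sensible precaution.

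**What to change.** Add one exclusion to section 4.3:

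> Known hypersensitivity to tamsulosin, or to PEAPROSTIL 600 or its listed ingredients (Serenoa repens, PEA); known symptomatic orthostatic hypotension; or, while taking an alpha-blocker, previous syncope or symptomatic hypotension.

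State that it is checked from the T0 allergy, therapy and history data before allocation, and that it applies whatever arm the man would enter.

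Two details of the wording matter. It names the listed ingredients because section 3.1 gives no full excipient list against which a broader clause could be checked. It ties syncope to alpha-blocker use so that a man who once fainted for another reason is not excluded. Earlier stopping for a tolerability effect such as an ejaculation disorder would not exclude.

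The cost is one line in section 4.3 and one eligibility checkbox on the CRF, with no new procedure. The downside is a small, unknown number of screen failures to replace. The sample size and the analysis stay as they are.

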## 5. Study procedure

### 5.1 Data Collection Method

Each patient participating in the study will be uniquely identified by an alphanumeric code. All the data required by the protocol, relating to the patient, to the medical record, to the therapeutic intervention, to the checks following discharge from the hospital, will be recorded by a co-investigator who will directly follow the study and its correct conduct for its entire duration. All data will initially be recorded on forms in paper format which will form the data collection folder (CRF).

A file containing all completed forms and signed informed consent will be kept for each patient.

Information concerning patients (identification codes, personal data, medical records, consent, information privacy policy) will be kept by the Investigator in special confidential archives (patients file) to guarantee the privacy of the subjects and exhibited in the event of audits, inspections or monitoring visits. All the variables under study will be entered in a dedicated and password-protected database, kept at S.C.D.U. Urology, The database will be shared on a cloud-protected server with the Biostatistics department of the University of Catania which will carry out the statistical analysis ([name]). The Investigator and co-Investigators will be the only ones to have access to the database.

#### 5.1.1 Method of randomization

Randomization will take place in a 1:1:1 pattern. Based on considerations clinical-scientific inherent to the typology of patients and to the clinical reality, the design experimental above currently corresponds to the best possible.

## 5.2 Pre-treatment assessment

All patients will undergo an accurate analysis of the following parameters (T0).

- Personal data: identification number and initials of the patient's name and surname, date of birth, telephone number and e-mail address.
- General characteristics: gender, weight, height, smoker, coffee and/or tea intake, allergies, job, sport, diabetes mellitus.
- Medical therapy in progress.
- Remote pathological history: previous surgical interventions, underlying pathologies and number of deliveries.
- Past pathological history and diagnosis: starting date and type of symptomatology
- Assessment of quality of life (QoL questionnaire).
- Voiding assessment (IPSS questionnaire)
- Physical examination: abdominal, urological including rectal examination.
- Uroflowmetry (morphology of the curve, Qmax, Vol, RPM-residual evaluation post urination)

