#### 5.4 Post-treatment evaluation protocol

All the variables will be collected by a co-investigator of [name] team during check-ups at pre-established intervals of 1, 3, 6 and 12 months (T1, T2, T3 and T4 respectively) and will be reported in the specific data collection folder (CRF).

- at 1 month (T1), 3 months (T2), 6 months (T3) and 12 months (T4):
- Personal data: identification number and initials of the patient's name and surname, date of birth, telephone number and e-mail address
- Medical history: IPSS, SF-36
- Physical examination: abdominal, urological including rectal examination
- Uroflowmetry: morphological analysis of the flow curve, Qmax, Volume of urine emptied, RPM).

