#### 6. Sample size and statistical analysis of the data

A total of 250 patients will be recruited. The sample analysis was performed by the "GF Ingrassia" Department of Medical, Surgical Sciences and Advanced Technologies of the University of Catania. In particular, the design foresees a 1:1:1 randomization process in 3 arms. Expect a difference of at least 2 points in IPSS and Qmax and a standard deviation of 4, as described in previous studies (Morgia et al., 2014; Alcaraz et al., 2016), it is necessary to enroll 250 patients to obtain a power 90% statistic at a significance level of 0.05.

The statistical analysis of the data collected during the study, according to an intention-to-treat procedure, will be performed using statistical software such as IBM SPSS statistics version 23.0. The variables that will be collected in order to evaluate the efficacy of the therapy will be: chronological age, weight, BMI, smoking, diabetes, PSA, IPSS, Postvoiding Residual, Qmax, QMed, Voided volume, SF-36 score. A descriptive analysis of the patients included in the three arms will be performed using the appropriate frequency measures and indices of central tendency and dispersion. Considering one pair of the three arms at a time (1 vs. 2; 1 vs. 3; 2 vs. 3), the qualitative variables will be compared using the chi-squared test; the quantitative variables will be

compared using Student's t-test. The level of significance will be set at  $p < 0.05$ . For the variables that will be significant in the univariate analysis, multivariate analyzes will be performed using appropriate regression models to control for the effect of the covariates.

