## 10. Abbreviations index

LUTS: low urinary tract symptoms

BPH: benign prostatic hypertrophy

PSA: prostate specific antigen

IPSS: International Prostatic Symptoms Score

QoL: quality of life questionnaire

CO2: Carbon dioxide

PEA: Palmitoylethanolamide

Qmax: maximum flow

5-ARI: 5 $\alpha$ -reductase inhibitors

DE: erectile dysfunction

RPM: post-voiding residue

Vol: volume

Cr: creatininemia

eGFR: glomerular filtration rate

UTI: urinary tract infection

CRF: data collection folder

TRUS: transrectal ultrasound

DHT: dihydrotestosterone

Echo: ultrasound

s: seconds

ml: millilitres

ng: nanograms

T0: zero time

T1: 1 month

T2: 3 months

T3: 6 months

T4: 12 months

Novara, 17/02/2021 [name]

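### Does the generic quality-of-life entry at T0 leave the SF-36 without a baseline, and PSA without a visit?

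*Combined protocol and SAP*

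**What the plan says.** Section 2.1 defines the primary outcome partly "in terms of subjective improvement of urinary symptoms by performing IPPS and SF-36 questionnaires", and Section 2.2 repeats this for the three-arm comparison. The follow-up list in Section 5.4 has "Medical history: IPSS, SF-36" at each of T1 to T4 (1, 3, 6 and 12 months). Section 6 lists among the variables for evaluating efficacy "PSA, IPSS, Postvoiding Residual, Qmax, QMed, Voided volume, SF-36 score".

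The T0 list in Section 5.2 gives the IPSS by name, but for quality of life it has only "Assessment of quality of life (QoL questionnaire". The abbreviations index offers "QoL: quality of life questionnaire" and has no SF-36 entry. Neither visit list mentions PSA or QMed. Section 5.1 states that "All the variables under study will be entered in a dedicated and password-protected database".

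**The concern.** An outcome described as improvement needs a starting value. If the T0 questionnaire were something other than the SF-36, the trial would hold a T0 score with no follow-up and an SF-36 series with no baseline. Change on the SF-36 could not be computed, nor could the analysis adjust for its baseline. The missing values could not be recovered once treatment had begun.

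PSA raises a smaller question of the same kind. It is an analysis variable with no stated visit, so its role as a baseline characteristic or a repeated measurement is not written down. QMed is likewise analysed without being named at any visit.

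**Working it through.** **1. The lists side by side.**

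| Item | Outcomes (2.1, 2.2) | T0 (5.2) | T1–T4 (5.4) | Analysis list (6) |
|---|---|---|---|---|
| IPSS | yes, spelt IPPS | yes | yes | yes |
| Qmax | through uroflowmetry | yes | yes | yes |
| Post-void residual | yes | yes, as RPM | yes, as RPM | yes |
| SF-36 | yes | generic label only | yes | yes |
| PSA | no | no | no | yes |
| QMed | not by name | not by name; uroflowmetry done | not by name; uroflowmetry done | yes |
| BMI | no | not by name; weight and height recorded | no | yes |

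Three things follow.

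- The protocol uses different labels for one item elsewhere: IPPS for IPSS, and RPM for post-void residual. A generic label for the SF-36 fits that habit.
- The analysis list was not written to match the visit lists word for word. BMI is not named at T0 but follows from weight and height. QMed stands between Qmax and voided volume, so it reads as one more value from a test done at all five visits.
- Section 5.2 is not exhaustive. Section 4.2 requires prostate volume "assessed by transrectal ultrasound (TRUS", and Section 5.2 does not list it. Absence from that list is therefore weak evidence that an item is not collected.

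**2. Which instrument at T0?** The SF-36 is the only quality-of-life instrument the protocol names, and the primary outcome asks for "subjective improvement of urinary symptoms by performing IPPS and SF-36 questionnaires". Both point to the SF-36 at T0. This is an inference; no sentence states it.

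**3. PSA.** In Section 6 it follows age, weight, BMI, smoking and diabetes, and precedes the outcome measures. Section 1 describes it as part of the diagnostic work-up. Sections 2.1 and 2.2 do not name it as an outcome. A baseline characteristic is the natural reading, and no efficacy conclusion rests on it.

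**4. What the sample size rests on.** Inputs from Section 6: difference 2, SD 4, 90% power, significance level 0.05 (taken as two-sided), three equal arms.

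- n per arm = 2 × 4² × (1.960 + 1.282)² / 2² = 84.1, or 85 rounded up; 3 × 85 = 255, close to the stated 250.
- At 83 per arm the power is 0.896.

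The stated size is thus reproduced from IPSS and Qmax alone. No SF-36 or PSA assumption enters it.

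**5. Size under the unfavourable reading.** Suppose the T0 questionnaire is not the SF-36. Assume equal variances at baseline and follow-up, and correlation ρ between them of 0.3, 0.5 or 0.7. The documents give no value for ρ.

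| ρ | Follow-up only vs adjusted variance, 1/(1−ρ²) | Follow-up only vs change-score variance, 1/(2(1−ρ)) | Detectable difference with adjustment |
|---|---|---|---|
| 0.3 | 1.10 | 0.71 | 0.480 SD |
| 0.5 | 1.33 | 1.00 | 0.436 SD |
| 0.7 | 1.96 | 1.67 | 0.359 SD |

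Without a baseline, at 83 per arm and 90% power, the detectable difference is (1.960 + 1.282) × √(2/83) = 0.503 SD. The last column multiplies this by √(1−ρ²).

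Against change scores, follow-up values alone are more precise at ρ = 0.3, equal at 0.5 and less precise at 0.7. Section 6 plans pairwise Student's t-tests. Regression follows only for variables significant in those tests, and its covariates are not named. The adjusted column is therefore precision the plan never claimed.

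**The case for a change.** The best case for a change starts from the T0 list itself. It names the IPSS, so a generic entry on the next topic stands out. The words on timing in Section 2.1 (before and during treatment) attach grammatically to uroflowmetry, so they do not prove a baseline SF-36. Section 5.2 also asks for number of deliveries in a trial restricted to men, which suggests text carried over from another study, and the quality-of-life line could have come with it. Data go first onto paper forms, so a form built literally from Section 5.2 would repeat the ambiguity for every patient. The loss could not be undone, and a line edit would prevent it.

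Part of this stands: the label is not tied to an instrument anywhere, and naming it would cost almost nothing. But the signs of carried-over text cut the other way as well. A loosely worded list is poor evidence that a second, unnamed questionnaire was deliberately chosen for T0. For harm to follow, the instrument must differ, and the analysis must depend on a baseline score that Section 6 does not call for. The documents support neither step.

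**Conclusion.** The concern does not call for a change to the plan. It is a loose label and an unstated time point, which the study team and analyst can fill sensibly: SF-36 at T0, PSA as a baseline characteristic, QMed from the uroflowmetry. On that reading nothing is lost.

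On the unfavourable reading, SF-36 change from baseline would be unavailable, but randomisation keeps the between-arm comparison of follow-up scores unbiased. The loss would be one of precision on the SF-36 only, from about 10% more variance than an adjusted analysis (ρ = 0.3) to about double (ρ = 0.7). Those figures depend on assumed correlations and on an adjustment the plan does not specify, and no SF-36 effect size or SD is given against which to judge them. IPSS, Qmax and the post-void residual are scheduled at T0 and at every follow-up visit, so the rest of the primary outcome is untouched.

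The conclusion rests on the inference that the generic T0 entry means the SF-36. It would need revisiting only if the case report form showed a different questionnaire at T0.
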